Study Population:	The subject population will consist of subjects with operable bilateral cataracts in each eye. Up to 539 subjects are to be enrolled, with 501 subjects planned to undergo phacoemulsification cataract surgery with IOL implantation in both eyes. Prior to cataract surgery in the first operative eye, subjects will be randomly assigned at a 2:1 ratio to receive either the investigational FINEVISION HP or the control IOL, Alcon AcrySof SN60AT [REDACTED] IOL. The second operative eye will undergo cataract surgery 7 – 30 days afterwards, with the same model IOL implanted.
Phase:	Pivotal
Description of Sites/Facilities Enrolling Participants:	Subjects will be enrolled at up to 24 study sites and surgeries will be performed in ambulatory surgery centers or hospitals. All study sites and surgery centers will be located in the United States. Each site will be encouraged to randomize a minimum of 20 subjects, and no site will randomize more than 25% of the total number of randomized subjects.
Description of Study Intervention:	The study intervention is an IOL to be implanted via routine small incision cataract surgery. Subject eyes in the test arm will be implanted with an investigational trifocal IOL, while the eyes in the control arm will be implanted with a commercially available monofocal IOL. IOLs are implantable medical devices intended for long term use over the lifetime of the subject.
Study Duration:	Study duration is estimated to be approximately 24 months based on an estimated enrollment period of 10 months and subject participation period of 14 months (calculated as the difference between the time of the Preoperative Visit to completion of 12-month follow-up on the second operative eye)
Participant Duration:	It is estimated that the duration of each subject's participation in the study will be approximately 14 months (calculated as the difference between the time of the Preoperative Visit to completion of 12-month follow-up on the second operative eye).

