## 7 PARTICIPANT DISCONTINUATION/ WITHDRAWAL

### 7.1 PARTICIPANT DISCONTINUATION/ WITHDRAWAL FROM THE STUDY

Discontinued subjects are those who withdraw from the study after the study informed consent document is signed and before the final visit is completed. Subjects who sign the study consent document but fail to meet eligibility criteria or withdraw prior to study IOL implantation in the first eye shall be considered discontinued due to screen failure.

A subject may be discontinued prior to the final study visit for any of the following reasons, including but not limited to:

- Screen failure
- Adverse event(s); note that subjects should be followed within the study until adverse event resolution or stability
- Investigator’s request (e.g. medical decision)
- Voluntary withdrawal (subject’s request)
- Death
- Study terminated by Sponsor
- Loss to follow-up

Prior to discontinuing a subject, every effort should be made to contact the subject to schedule a final study visit and obtain as much follow-up data as possible. Discontinued subjects should thereafter be followed outside of the study protocol according to the Investigator’s normal standard of care.

The reason for participant discontinuation or withdrawal from the study will be recorded on the Exit Case Report Form (CRF).

Randomized subjects who do not receive a study IOL may be replaced. Randomized subjects who receive a study IOL and are discontinued or withdraw from the study afterwards will not be replaced.

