## 5. Sample Size and Power Considerations

As specified in ANSI Z80.12:2007 (R2017) –C.4, a minimum of 300 subjects implanted with the investigational IOL and 150 subjects implanted with the comparator IOL must be available for analysis at Visit 5 (postoperative days 330-420).

To consider the potential loss of subjects between the time of enrollment and study completion, a total of approximately 501 subjects will be randomized and undergo surgery in this study. It is assumed that of approximately 501 subjects who undergo surgery, 51 subjects (10%) will be discontinued prematurely or lost to follow-up. Subjects will be randomized to receive either the investigational or comparator IOL in a 2:1 ratio. Of 501 subjects who undergo surgery, approximately 334 subjects will receive the investigational IOL, and 167 subjects will receive the comparator IOL. Expecting a screen failure rate of 7%, up to 539 subjects will be enrolled in the study to have 501 subjects randomized and scheduled for surgery.

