### Primary Strategy

1. Withdrawal due to physician decision: missing data assumed to be MNAR. Control-based multiple imputations will be completed for superiority hypotheses and treatment-based multiple imputations will be completed for non-inferiority hypotheses. [hypothetical strategy]
2. Missing data without withdrawal or withdrawal due to reasons other than due to physician decision: missing data assumed to be MAR. Treatment-based multiple imputations will be completed. [hypothetical strategy]

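### Protocol 7.1 lets a subject with a study lens be exited for an adverse event or at the investigator's request without securing Month 6 and Month 12 data; the main exposure is the SSI co-primary, and the remedy is cheap.

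*Protocol*

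**What the plan says.** Protocol 7.1 introduces its exit reasons with "A subject may be discontinued prior to the final study visit for any of the following reasons, including but not limited to". Two of them matter here. One is "Adverse event(s); note that subjects should be followed within the study until adverse event resolution or stability". The other is the investigator's request, with a medical decision as the only example. Before exit, "every effort should be made to contact the subject to schedule a final study visit and obtain as much follow-up data as possible". After it, "Discontinued subjects should thereafter be followed outside of the study protocol according to the" investigator's usual care. A subject who has received a study lens and then leaves is not replaced.

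The Protocol synopsis says of the intervention that "IOLs are implantable medical devices intended for long term use over the lifetime of the subject". After implantation the remaining visits therefore mostly assess a device already in place. Protocol 8.6 does provide for removal or exchange.

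On missing data, SAP 8.2 states "Withdrawal due to physician decision: missing data assumed to be MNAR". For DCNVA this leads to control-based imputation. For BCDVA the primary imputation is treatment-based, and the BCDVA code in SAP 13.1 does not split by reason for withdrawal. Imputation from the worse half of the subject's own arm is a sensitivity analysis only. Withdrawals for adverse events are treated as missing at random in every analysis. These rules cover the primary and secondary effectiveness analyses. SAP 15.1 gives no corresponding rule for SSIs; a subject with none is coded N.

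SAP 5 assumes that "51 subjects (10%) will be discontinued prematurely or lost to follow-up", with no breakdown by reason.

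**The concern.** In a drug trial, discontinuation usually means stopping the drug, and data collection can continue. Here there is normally nothing to stop once the lens is in, so discontinuation in 7.1 amounts to ending data collection. The two safeguards do not reach the endpoint visits. An adverse event that settles at Month 3 meets the follow-up condition, and the final visit is an effort that is not tied to the Visit 4 or Visit 5 window.

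Exits of this kind may be related to outcome, and the SAP assumes as much for physician-decision withdrawals. For visual acuity there is at least an imputation rule. For SSIs there is none: an intervention that takes place after exit, under routine care, need not enter the study record, and the subject would then count as a non-event. No analysis can recover an event that was not observed.

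**Working it through.** **Inputs.** Protocol 9.2 and SAP 5: 501 operated (334 test, 167 control); 51 losses assumed; 300 and 150 at analysis; BCDVA SD 0.10 and margin 0.10 logMAR, one-sided alpha 0.05; DCNVA difference -0.10 and SD 0.14, two-sided alpha 0.05; SSI margin 0.014, true rate 0.001 in both arms, one-sided Farrington-Manning test at 0.05. The number of exits for adverse events or at the investigator's request is not given and is assumed below.

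**The plan's own figures.** 501 - 51 = 450 = 300 + 150, and 51/501 = 10.2%, so the allowance meets the stated minimum with nothing to spare. The BCDVA standard error is 0.10 × √(1/300 + 1/150) = 0.010, so the margin is 10 standard errors and power exceeds 99%, as stated. For SSIs the asymptotic power is 77.9% against the plan's approximately 80%; the point does not depend on that difference.

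**BCDVA.** Bias in the test mean = (exits/334) × (true deficit relative to the imputed value).
- 10 exits, 0.1 logMAR each: 10 × 0.1/334 = 0.003.
- 17 exits, 0.3 logMAR each: 17 × 0.3/334 = 0.015.

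With no true difference otherwise, the room before non-inferiority is lost is 0.10 - 1.645 × 0.010 = 0.0836. If all 34 expected test losses were of this kind, each eye would have to be 0.0836/(34/334) = 0.82 logMAR worse than imputed. The bias would matter only if the truth lay near the margin. For example, 17 exits at 0.1 logMAR (bias 0.0051) would raise the one-sided error at the margin from 0.05 to Φ(0.51 - 1.645) = 0.13.

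**DCNVA.** The standard error is 0.14 × √(1/300 + 1/150) = 0.014. The room is 0.10 - 1.96 × 0.014 = 0.0726, so 34 missing test eyes would each have to be 0.0726/(34/334) = 0.71 logMAR worse than imputed.

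**SSI.** With no control events and few test events, the restricted estimates under the null hypothesis are 0.014 (test) and 0 (control). The statistic is then z = (x/n - 0.014)/√(0.014 × 0.986/n), where x is the number of test events and n the number of test eyes.

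| Test / control eyes | Test events | z | One-sided p | Non-inferior? |
|---|---|---|---|---|
| 334 / 167 | 0 | -2.18 | 0.015 | yes |
| 334 / 167 | 1 | -1.71 | 0.043 | yes |
| 334 / 167 | 2 | -1.25 | 0.106 | no |
| 300 / 150 | 0 | -2.06 | 0.0195 | yes |
| 300 / 150 | 1 | -1.57 | 0.058 | no |

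The 334/167 rows apply if exited subjects stay in the denominator as N, which is how the Safety Set definition and the coding in SAP 15.1 read. The 300/150 rows are the planned completers. On either basis a single test-arm event, seen or unseen, separates a pass from a failure.

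**The case against.** The strongest reply is that 7.1 only permits these exits, and that retention is otherwise the default. Protocol 5.3 keeps a subject whose second-eye implantation fails in the study for all first-eye visits. Protocol 5.5 sets out retention steps. Protocol 8.7.5 requires events ongoing at exit to be followed to resolution or stabilisation. The likely route to an optical SSI is persistent visual symptoms, and 7.1 already keeps an adverse-event case in the study until it resolves or is stable. SSI fragility is also a feature of a test with almost no expected events: at the planned rate of 0.001, 17 exits carry 17 × 0.001 = 0.017 expected SSIs. Voluntary withdrawal and loss to follow-up carry the same risk. All of this stands, and it limits the size of the point. It does not remove it, because none of these provisions secures Month 12 SSI status for a subject exited earlier.

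A reader might infer more than the documents support:
- *That 7.1 itself creates informative missing data.* It allows it; neither the number of exits nor their relation to outcome is given.
- *That an unmasked investigator decides.* Protocol 6.3 names vision assessors and subjects as masked and exempts the investigator from the restriction on communication. That the investigator is unmasked is a fair inference, not a statement.
- *That the lens always stays in the eye.* Protocol 8.6 and 8.6.2 provide for removal and replacement.
- *That those who leave are the ones with poor visual results.* Adverse events include non-ocular events, and a medical decision need not concern the eye.

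**Conclusion.** This is a gap in data collection that is cheap to close. It is not a flaw that undermines the co-primary effectiveness results. Under the assumed 10 to 17 test exits with deficits of 0.1 to 0.3 logMAR, the BCDVA bias is 0.003 to 0.015 against a margin of 0.10, and DCNVA is similarly robust at the planning effect. Reading the gap as a threat to those two conclusions is not supported. The exposure that counts is the SSI co-primary. It has no rule for early exit, and with no control events one unseen optical SSI in the test arm can turn a failure into a pass. That is unlikely at the planned event rate; how much likelier an SSI is among exited subjects cannot be judged from the documents. Contrast sensitivity and the QoV questionnaire also lose Month 12 data, but both are descriptive.

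**What to change.** In Protocol 7.1, state that once a study lens is implanted in the first eye, an adverse event, an SSI or an investigator's medical decision may stop individual study assessments but does not by itself end follow-up. Say that this also governs the open-ended introduction to the list; deleting two items from a non-exhaustive list would not close the route. Such subjects stay scheduled for Visits 4 and 5 unless they withdraw consent, die, are lost to follow-up or the study is terminated. The rule in Protocol 5.3 for a failed first-eye implantation is unchanged, and clinical care decisions remain with the investigator.

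For anyone who stops attending without withdrawing consent, record SSI and adverse-event status through Month 12 by contact or chart review. Keep the SAP 8.2 imputation rules as a fallback for visual acuity.

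The cost is a paragraph of protocol text, an option on the Exit CRF and a little extra contact work at sites. A few subjects with medical problems would be asked to keep attending visits that are already scheduled, and they may decline.

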## 7.2 LOST TO FOLLOW-UP

The following actions must be taken if a participant fails to return to the clinic for a required study visit:

- The site will attempt to contact the participant by telephone, electronic, or regular mail to reschedule the missed visit. At least 3 documented attempts to contact the subject must be made. If the subject does not respond to these attempts, a certified letter must be sent to the participant's last known mailing address.
- Should the participant continue to be unreachable, he or she will be considered to have withdrawn from the study with a primary reason of lost to follow-up.]

These actions will be recorded in the source documents and a copy of the certified follow-up letter maintained in the source documents. The date of discontinuation for subjects lost to follow-up will be 7 calendar days after the date that the unanswered certified letter was sent.

## 8 STUDY ASSESSMENTS AND PROCEDURES

Study participants will be evaluated at a Preoperative Visit. For subjects who qualify for further study participation, the primary eye will be determined, the subject will be randomized to receive the assigned study IOL, and surgery will be scheduled to occur between 1 and 90 days after the Preoperative visit.

Cataract surgery/IOL implantation will be performed for the primary eye and the subject will be scheduled to return for follow-up visits and examinations at the Day 1, Week 1, Month 1, Month 6, and Month 12 time periods, consistent with study visits described in ISO 11979-7 (Form 0 through Form 5). Cataract surgery/IOL implantation in the second operative eye will be scheduled 7 – 30 days after primary eye surgery in a manner such that follow-up examinations for the second operative eye may be performed when the subject returns for scheduled primary eye visits. Data collected from each visit, including any abnormal findings, will be documented in the source records and recorded on study eCRFs.

The timing and frequency of assessments/procedures to be performed at each visit is outlined in the SoA.

Methodology for study examinations is presented in the Manual of Procedures.

### 8.1 PREOPERATIVE VISIT (DAY -90 TO DAY -1): VISIT 0

The Preoperative Visit must occur no more than 90 days and no less than 1 day prior to the Operative Visit. Informed consent must be obtained prior to performing study-specific procedures not part of the

investigator's routine standard of care. Subjects who sign the ICF will be given a unique 4-digit screening number, where the first two digits corresponds to the site number.

At this visit, the following activities will be performed:

- Ocular and significant non-ocular medical history\*
- Projected Visual Acuity\*
- UCDVA\*
- BCDVA\*
- Target Refraction/IOL power calculation/Axial Length/Anterior Chamber Depth (biometry)\*
- Keratometry\*
- Corneal Topography\*
- Manifest Refraction (ETDRS)\*
- Photopic/mesopic pupil size\*
- Intraocular Pressure\*
- Slit Lamp Exam\*
- Dilated Fundus Exam\*

*\* These assessments, if performed during routine standard of care exams up to 90 days before the subject Preoperative Visit, may be used as qualifying preoperative assessments prior to consent. All study specific evaluations not included in a routine cataract evaluation must be performed in the preoperative time period (Day -90 to Day -1).*

For those determined to be eligible for cataract surgery/IOL implantation, the eye with the worse BCDVA will be scheduled for surgery first. If BCDVA is the same for both eyes, the right eye will be implanted first. The randomization assignment will be determined indicating which IOL will be used, and the subject's surgery will be scheduled.

## 8.2 OPERATIVE VISIT (DAY 0): VISIT 00 A/B

The Operative Visit for the first operative eye must occur on Day 0. The Operative Visit for the second operative eye must be scheduled between Days 7 – 30, inclusive.

At the Operative Visit, prior to surgery, subjects will be assessed to reconfirm eligibility and any changes in concomitant medications or medical/ocular conditions will be recorded on the appropriate CRF. If the subject is determined no longer to be eligible, he/she will be discontinued from the study prior to cataract surgery and considered a screen failure.

If operative complications prevent implantation of the investigational IOL (see Section 5.3 – Reasons Not to Implant a Study IOL), a non-study IOL may be implanted instead. Subjects who were not exposed to the study IOL will be exited from the study and followed per the investigator's standard of care.

No additional refractive procedures are to be performed during the operative procedure or throughout the postoperative study period.

The Investigator should refer to the Manual of Procedures for more detailed guidance on FINEVISION HP implantation and AcrySof SN60AT [REDACTED] implantation. Subjects must be targeted as closely as possible for emmetropia. Surgeons may use their personalized A-constant for model SN60AT [REDACTED].

For study visits designated A or B, 'A' represents the first eye implanted (Eye A), and 'B' represents the second eye implanted (Eye B). Monocular assessments will be performed at **Visits 00 A/B, 1 A/B, 2 A/B, and 3 A/B** for only **Eye A** or only **Eye B**, respectively, unless binocular assessments are specified (See Schedule of Activities, Section 1.3). At Visits 4 and 5, monocular assessments and binocular assessments will be completed for both eyes.

### 8.3 POSTOPERATIVE VISITS: VISIT 1 THRU VISIT 5

Postoperative visits should be scheduled according to the following visit window schedule:

- Visit 1 A: 1-2 days after surgery on the first eye
- Visit 1 B: 1-2 days after surgery on the second eye
- Visit 2 A: 7-14 days after surgery on the first eye
- Visit 2 B: 7-14 days after surgery on the second eye
- Visit 3 A: 30-60 days after surgery on the first eye
- Visit 3 B: 30-60 days after surgery on the second eye
- Visit 4: 150-180 days after surgery on the first eye
- Visit 5: 360-420 days after surgery on the first eye

IOL implantation in the second operative eye is to be scheduled between 7 to 30 days after IOL implantation in the first operative eye. Subsequent Post-Op visits for the first and second eye are to be conducted as separate visits for Visits 1-3. Visits 4 and 5 must be conducted for both eyes at the same time based on timing from when the first eye was implanted.

Refer to the Schedule of Activities in Section 1.3 and the MOP for detailed procedures to be performed at these scheduled postoperative visits.

### 8.4 UNSCHEDULED VISITS

Unscheduled visits are those which are not required by the study protocol, but which occur due to an ocular intervention or a subject complaint regarding their eye.

If a subject visit occurs between any regularly scheduled visits, this visit is to be documented as an Unscheduled Visit. During all unscheduled visits, the Investigator should conduct assessments as appropriate given the subject's condition. Mandatory assessments include:

- Patient Reported Outcomes Questionnaires
- Concomitant medication
- Ocular and non-ocular medical history
- Manifest refraction
- BCDVA at 4 m (photopic) monocularly, binocularly for each implanted eye
- UCDVA at 4 m (photopic) monocularly, binocularly for each implanted eye
- Keratometry
- Slit lamp exam
- Posterior capsule assessment
- IOL observations
- IOL tilt and decentration grading
- Intraocular pressure
- IOL Axis Orientation (retroilluminated slit lamp photo) – selected sites only
- Fundus exam with dilated pupil
- Adverse events
- Device deficiencies

The Investigator may perform additional procedures for proper diagnosis and treatment of the subject according to SoA in Section 1.3. The Investigator must document this information in the subject's source documents and record it on the USV eCRF.

If, during an Unscheduled Visit, the subject is discontinuing from the study, the Investigator must complete the Exit CRF.

Visits intended to fulfill scheduled visit requirements that fall outside the designated scheduled visit window are not Unscheduled Visits. In these cases, the visit data will be collected and transcribed to the appropriate scheduled visit CRF and a protocol deviation should be reported, if applicable.

## 8.5 CONCOMITANT MEDICATION

Documentation of all medications used by the subject within 30 days of the Preoperative Visit and during the study will be entered in the Concomitant Medication CRF. Pre-, intra-, and postoperative medications may be administered per the Investigator's standard of care and documented in source documents only (not to be entered in CRFs). A complete list of the Investigator's standard regimen of these medications will be provided to the Sponsor or its designee and approved by the Medical Monitor prior to initiation of the study. Medications known to interfere with visual performance, pupil dilation, or iris structure are prohibited for the duration of the study.

## 8.6 SECONDARY SURGICAL INTERVENTION (SSI)

The study Investigator must make an assessment of the subject to determine if a secondary surgical intervention (SSI) is needed. This assessment should be based on the Investigator's assessment of the subject's clinical outcome, subjects feedback related to visual symptoms, and other reasons, such as observed retained lens fragments. The Investigator's assessment of the need for SSI should be based on a thorough examination including diagnostic testing as appropriate. Consideration of BCDVA, IOL stability and subjective complaints such as blurred vision or visual disturbances should be considered, with an assessment of the potential risks and benefits associated with the SSI.

The Investigator must assess if an SSI is related to the optical properties of the IOL. An SSI is considered related to the optical properties of the IOL if the SSI is due to subject intolerance of visual symptoms not adequately improved by spectacle correction.

Situations requiring SSIs that are not considered related to the optical properties of the IOL include:

- Posterior capsular opacification (PCO; note that YAG for PCO is not considered an SSI but an analysis of rates will be performed)
- Macular edema confirmed by optical coherence tomography and/or fluorescein angiography
- Corneal disorders (e.g., dry eye syndrome, edema, and corneal irregularities)
- Pre-existing or newly developed ocular pathologies, including those related to decentration, tilt or rotation of the IOL requiring reoperation
- Surgical complications noted at the operative visit that may reasonably be expected to affect postoperative outcomes

Secondary IOL interventions should be categorized as IOL exchange (the investigational device is replaced with the same lens model), IOL removal (the investigational device is removed and replaced with a non-investigational lens or no lens is implanted), IOL repositioning (the existing IOL is surgically moved to another location or rotated), or other. Indications for device exchange, removal, or repositioning will be recorded in the CRF.

The investigator should consult with the Medical Monitor to determine if an SSI is warranted. If there is any uncertainty as to whether the SSI is related to the optical properties of the IOL or to some other unrelated factor, the Investigator should consult with the Medical Monitor. The Investigator should determine the most suitable SSI procedure for each case. Note that limbal relaxing incisions during cataract surgery and refractive procedures to address residual refractive error are disallowed by the protocol.

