## 6.3 MEASURES TO MINIMIZE BIAS: RANDOMIZATION AND MASKING

Subjects will be randomly assigned to receive either the investigational FINEVISION HP IOL or the AcrySof monofocal IOL in both eyes according to the randomization schedule (2:1 ratio) provided. Randomization will be stratified by site. The randomization schedule will be created using computer-generated randomization methodology by an independent statistician who is not involved in the day-to-

day conduct of the study. Randomization is to occur following the completion of informed consent and screening procedures.

In order to minimize bias, site personnel performing postoperative study assessments of visual performance, including manifest refraction, visual acuity, defocus curve testing and contrast sensitivity will be masked to subject treatment assignment until after the final database lock (“masked assessors”). Any unmasking of the masked assessor or any study subjects must be reported to the Sponsor. Every attempt should be made to have the same masked assessor perform the same postoperative measurements for an individual subject throughout the subject’s study participation.

Subjects will also be masked to their assigned treatment group (test or control group). Any material that may indicate the subjects’ assigned treatment, e.g., packaging, documents, etc., should be removed from areas where subjects and/or masked personnel may see it. Unmasked personnel should further be instructed to avoid conversation and communication with masked personnel, subjects and persons other than the study investigator regarding subjects’ assignments, outcomes, clinical courses and all other information potentially relevant to the study and its conduct.

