#### 3.5.2 PRIMARY SAFETY HYPOTHESES

##### 3.5.2.1 SECONDARY SURGICAL INTERVENTIONS

The null ( $H_{01s}$ ) and alternative ( $H_{11s}$ ) hypotheses for the first co-primary safety variable, cumulative rate of SSIs related to the optical properties of the FINEVISION HP trifocal IOL through Month 12 (Visit 5), are as follows:

$$H_{01s}: p_{t1s} - p_{c1s} \geq 0.014$$

$$H_{11s}: p_{t1s} - p_{c1s} < 0.014$$

where  $p_{t1s}$  and  $p_{c1s}$  denote the population proportion of first operative eyes at Month 12 (Visit 5) requiring SSI related to the optical properties of the IOL for the test and control IOLs, respectively.

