### **15.1 Primary Safety Analyses**

The co-primary safety endpoints are:

- Cumulative rate of SSIs related to the optical properties of the IOL in first operative eyes through Month 12 (Visit 5)
- Mean monocular distance contrast sensitivity (mesopic with and without glare at 1.5, 3, 6, and 12 cpd measured at 2.5m, and photopic with and without glare at 3, 6, 12, and 18 cpd, measured at 2.5 m) in first operative eyes at Month 12 (Visit 5)

The analyses of co-primary safety variables will be based on first operative eyes and repeated as supportive analyses using second operative eyes as well as all operative eyes.

Secondary surgical interventions related to the optical properties of the IOL will be evaluated using discrete summary statistics. Noninferiority of FINEVISION HP IOL compared to AcrySof® SN60AT [REDACTED] IOL in the proportions of first operative eyes with secondary surgical interventions related to the optical properties of the IOL will be evaluated using two-sided 90% Farrington method CIs around the difference in proportions between the FINEVISION HP IOL and AcrySof® SN60AT [REDACTED] IOL. If the upper limit of the CI is less than 0.014 (1.4%), then  $H_{01s}$  will be rejected in favor of  $H_{11s}$ , and the FINEVISION HP IOL will be considered statistically non-inferior to the AcrySof® SN60AT [REDACTED] IOL in rate of SSIs related to optical properties of the IOL.

SAS® code similar to the code below will be used to compute the Farrington CIs:

```
proc freq data = indata;
  table TRTAN * resp / nocol nopercent riskdiff(noninf margin = 0.014
method = fm column = 1) alpha = 0.05;
  ods output CrossTabFreqs = freqs(where = (resp = "Y")) PdiffNoninf =
cis;
run;

data freqs;
  set freqs;
  freq = Frequency;
  pct = RowPercent;
run;

/* Adjust CIs to convert limits to percentages and convert diff estimate, CI
for p_control - p_test to diff estimate, CI for p_test - p_control */
data cis;
  set cis;
  diff_pct = -100*Estimate;
  diff_ci_LCL = -100*UpperCL;
  diff_ci_UCL = -100*LowerCL;
run;
```

where

- TRTAN equals 1 for the test IOL (FINEVISION HP IOL) and 2 for the control IOL (AcrySof® SN60AT [REDACTED] IOL)
- resp equals "Y" if a subject has any SSIs related to the optical properties of the IOL or "N" if a subject has no SSIs related to the optical properties of the IOL.

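### Whether a first-eye SSI counts in the co-primary safety test rests on a label from an investigator who appears to be unmasked, and no planned between-arm test is independent of that label

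*Protocol*

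**What the plan says.** **The label.** Protocol 8.6: "The Investigator must assess if an SSI is related to the optical properties of the IOL". The criterion is that an SSI is related "if the SSI is due to subject intolerance of visual symptoms not adequately improved by spectacle correction". A list follows of situations requiring an SSI that do not count as optical, including corneal disorders such as dry eye, and pathologies linked to decentration or tilt.

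**The check on it.** The investigator should consult the Medical Monitor on whether an SSI is warranted. On relatedness, consultation is called for "If there is any uncertainty as to whether the SSI is related to the optical properties of the IOL or to some other unrelated factor". No masked or independent classification is described in the public text.

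**Masking.** Protocol 6.3: "site personnel performing postoperative study assessments of visual performance, including manifest refraction, visual acuity, defocus curve testing and contrast sensitivity will be masked". Subjects are masked too. The investigator is not named as masked. Unmasked staff are told not to discuss assignments with "masked personnel, subjects and persons other than the study investigator regarding" those assignments. SAP 16.9 has retinal-image clarity graded only in eyes with a multifocal lens, so whoever grades it knows the lens type.

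**The analysis.** In SAP 15.1 the response is Y "if a subject has any SSIs related to the optical properties of the IOL". Non-inferiority is declared if the upper limit of the two-sided 90% Farrington interval is below 0.014. The set is the Safety Set, with first operative eyes as the unit.

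**What else is reported.** All-cause SSIs, excluding posterior capsulotomies, are an ISO cumulative adverse event (Protocol 8.7.2.1). SAP 15.2 tabulates them by arm and tests each arm against the SPE rate.

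**The concern.** The other co-primary endpoints (BCDVA, DCNVA, contrast sensitivity) are measured by masked assessors. The SSI endpoint is the exception: a causal judgement by someone who appears to know the arm decides whether a performed surgery is an event. Protocol 2.3.1 names halos, glare and reduced contrast as multifocal risks that may lead to an SSI, so knowing the lens could influence that judgement. Events are expected to be very rare (0.001 per arm), so a single label can settle the test. At stake is the credibility of the SSI non-inferiority claim.

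**Working it through.** **1. Is the investigator masked?** No sentence says so either way. Three points lead to the inference that the investigator is not. The masked roles in Protocol 6.3 and SAP 4.5 are the visual-performance assessors and the subjects. The investigator is the one person excepted from the ban on discussing assignments. The grading in SAP 16.9 presupposes knowledge of the lens.

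**2. Is any planned analysis independent of the label?** The repeats in second eyes and all eyes, the pupil-size subgroups and the site summaries in SAP 15.1 use the same label. The ISO count in SAP 15.2 does not, but it tests each arm against a fixed rate. No between-arm interval is planned for it.

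**3. Formula.** Let d = x_t/n_t − x_c/n_c, and let p̃_t and p̃_c be the maximum-likelihood estimates restricted to p̃_t − p̃_c = 0.014. Then

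SE = √[p̃_t(1−p̃_t)/n_t + p̃_c(1−p̃_c)/n_c], z = (d − 0.014)/SE, upper 90% limit = d + 1.645·SE.

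**4. The plan's own figure.** Protocol 9.2 and SAP 5.2.1 give about 80% power at 300/150, rates 0.001 in both arms, margin 0.014, one-sided alpha 0.05. The asymptotic Farrington-Manning formula gives 77.9% and exact enumeration 77.2%. That is close to a figure stated as approximate, and nothing below depends on the gap.

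**5. Where the decision turns.** With no control event and the few test events tabulated here, the restricted estimates are p̃_t = 0.014 and p̃_c = 0.

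- 334/167 (planned implanted eyes, close to the Safety Set): SE = √(0.014 × 0.986/334) = 0.006429, and 1.645 × SE = 1.057%. Each test event adds 1/334 = 0.299%.
- 300/150 (planned completers): SE = √(0.014 × 0.986/300) = 0.006783, and 1.645 × SE = 1.116%. Each test event adds 1/300 = 0.333%.

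| Test v control events | 334/167 upper limit | 300/150 upper limit |
|---|---|---|
| 0 v 0 | 1.057% pass | 1.116% pass |
| 1 v 0 | 1.357% pass | 1.449% fail |
| 2 v 0 | 1.656% fail | 1.782% fail |
| 3 v 0 | 1.956% fail | 2.116% fail |
| 1 v 1 | 0.989% pass | 1.054% pass |
| 2 v 1 | 1.321% pass | 1.429% fail |
| 3 v 1 | 1.660% fail | 1.815% fail |

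Inverting the score test gives the same pass or fail at these boundaries.

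**6. How often a result sits at that boundary.** At the plan's rates (0.001 each), exact enumeration gives a 22.8% chance of failing at 300/150. In 19.6 of those 22.8 points (86%), one fewer test event would have passed. At 334/167 the figures are 3.44 of 3.85 points (89%). With an assumed true test rate of 0.010 against 0.001, the shares drop to 17% and 25%. These figures measure sensitivity to one label. They do not measure bias.

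**The case against.** **The rule is written down.** A lens removed for intolerable halos meets the positive criterion. The not-related list covers conditions that themselves require the SSI, so incidental dry eye or slight decentration is not an exclusion, and doubtful cases go to the Medical Monitor. This stands: the definition is usable. What remains is that the person applying it appears to know the arm, and a confident investigator does not trigger the check.

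**Nothing is hidden.** All SSIs and the events causing them are reported as adverse events, indications for exchange, removal or repositioning go on the CRF, and all-cause SSIs are shown by arm. This stands, and it limits the harm. It still gives no between-arm comparison free of the label.

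**Direction.** A reader might infer that mislabelling favours the trifocal, because optical SSIs arise mainly in that arm. The documents do not support this. An investigator alert to multifocal symptoms could as easily over-attribute an SSI to the optics, and no mislabelling rate is given.

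**Requiring versus having.** A reader might infer from the hypothesis wording ("requiring SSI related to the optical properties of the IOL for the test and control IOLs") that surgeries judged warranted but never performed should count. The objectives, variables and endpoints in both documents say cumulative rate of SSIs, and the SAP introduces this same hypothesis in those terms. The endpoint is surgeries performed, and the hypothesis is loosely worded.

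**Redaction.** Text after the bias-control statements in Protocol 4.1 and SAP 4.1 is blacked out, and the Medical Monitor section is empty in the public copy. A further safeguard cannot be ruled out.

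**Conclusion.** The point holds as a cheap improvement to a co-primary safety endpoint. The event label comes from an investigator who, by inference, is unmasked. Relatedness is reviewed only on uncertainty, and no planned between-arm test is free of the label. With no control event, the boundary lies between one and two test events at 334/167 and between none and one at 300/150.

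Two limits apply. One label changes the conclusion only at the boundary: at 334/167 with no control event, going from 3 to 2 test events still fails and from 1 to 0 still passes. A reader might also infer that a wrong SSI result could make the study a success. It could not, because Protocol 9.4.3 and SAP 13.1 make success depend on the two effectiveness endpoints alone. The consequence is confined to the SSI safety claim.

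The conclusion assumes that the investigator is unmasked, that the Safety Set is close to the planned numbers, and that the redacted text holds no masked classification.

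**What to change.** 1. **Protocol 8.6.** Before database lock, the Medical Monitor classifies optical relatedness for every first-eye SSI from a narrative with lens model and arm removed. If the Monitor already knows the arm, for example from having advised on whether the SSI was warranted, an existing sponsor medical reviewer who was not consulted on the case does it instead. Use this label in SAP 15.1 and keep the investigator's label as a sensitivity analysis.
2. **SAP 15.1.** Add a supportive 90% Farrington interval for the between-arm difference in all first-eye IOL removals, exchanges and repositionings, regardless of attributed cause. The existing code serves.
3. **Wording.** Align the hypothesis in Protocol 9.1 and SAP 3.5.2.1 with the endpoint, which counts SSIs performed. A run that adds surgeries judged warranted but not performed is not recommended, since it would rest on the same unmasked judgement.

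Cost: a short protocol clarification, one data item for the masked label, a few narratives and two extra runs. The masked label may give a less favourable SSI result. Sample size, margin and patient care do not change.
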